We are currently conducting 'think-aloud interviews' with PPIE members to obtain immediate reactions to all elements and materials of the study. We are using purposive sampling to ensure we interview young people from different cultural, ethnic and socio-economic groups focussing on economically disadvantaged young people (who are at increased risk of developing mental health problems). Although analyses is ongoing, we analyse, tabulate, and discuss potential changes with the co-production team until there are no further changes required. We aim to maximise accessibility, usability, and credibility of our materials via our co-production team throughout the present study.

3. Aims & Objectives

Overall aim: To develop, optimise and evaluate a novel, accessible, engaging public health intervention.

The following research questions are designed to enable us to achieve our aim:

- 1. What are the most acceptable, and engaging co-produced brief smart-phone-delivered interventions for insomnia and mental health symptoms for young people aged 14-18 (especially those from economically disadvantaged backgrounds)?
- 2. How should we adapt SHUTi (which works for adults), for young people so it is engaging for those with acute (6 weeks) insomnia symptoms?
- 3. Are automated mental health interventions that have been shown to work for young people presenting to mental health services, acceptable for this group of young people?
- 4. How effective is the detection of early mental health symptoms using insomnia symptoms?
- 5. Do mental health symptoms reduce following a) STEP 1 online advice on improving sleep hygiene and b) STEP 2 adapted modular SHUTi insomnia programme?
- 6. How do young people experience the technology?
- 7. What is the most effective method to communicate with young people and our stakeholders to ensure rapid dissemination and widespread national take up?

4. Methodology

Overarching Design

A stepped care approach improves access to appropriate care. We propose the following staged approach:

- STEP 1: Online advice on improving sleep hygiene provided as automated accessible audiovisual materials suitable for economically disadvantaged young people and those from different cultural backgrounds.
- STEP 2: If symptoms persist, participants will be offered adolescent SHUTi (automated iCBT for insomnia) delivered in 6 modules.

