- STEP 3: If participants are seeking further advice for their mental health, they will be signposted to *Bite Back* (a web-based well-being programme).

Optimisation and Evaluation

An observational cohort with integrated qualitative methodology will provide the infrastructure to develop the web-based applications, test the feasibility and acceptability of passive data collection, online screening and data linkage. Follow up questions on insomnia, anxiety and depression symptoms at 6-weeks, 6- and 12-months will enable us to test detection efficacy. We will synthesise quantitative and qualitative data to explore the acceptability and feasibility of recruitment, the web-based applications, data collected, and retention.

Recruitment:

Participants (aged 14-18) will be recruited through our established collaborations with:

- The Association of Colleges (https://www.aoc.co.uk) (93% of all further education and 6th form colleges).
- E-Act Multi-academy trust (https://www.e-act.org.uk/) who have links with academies throughout the UK.

Recruitment will focus on schools and colleges from across the UK, with the aim to ensure participation of CYP from diverse and disadvantaged backgrounds. A poster describing the study will be shared within each school/college to encourage young people to participate. By scanning a QR code, participants will be directed to the participant information sheet on their smartphones. If the poster is shared electronically, participants will be asked to type the relevant URL into their mobile browser or text the study mobile number (via Twilio) which will send an automated reply with a link to the online participant information sheet.

All participants will receive two £10 vouchers as a thank you for their time. One after their baseline survey, and another after their 6-week (second) survey. If a participant decides to participate in a one-to-one interview, they will be rewarded with a £40 voucher.

Sample size:

A sample size of 1000 is a pragmatic choice as an achievable recruitment target and sufficient to answer research questions. If we assume 20% attrition, recruiting 1000 young people will provide data

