on 800, of which 240 (30%) will have insomnia symptoms at enrolment and 180 (75%) will also have mental health symptoms. Of those with healthy sleep, if the incidence of acute insomnia (one month or less) is similar to adults then 150 -210 (27-37%) will develop insomnia each year (of which 72% will recover). A cohort of this size will put confidence intervals around these assumptions.

Inclusion and Exclusion Criteria

Included: Young people:

- Aged 14-18,
- Who attend secondary school or college,
- Who have a mobile phone.

Excluded: Young people:

- Aged 14 or 15 who do not have the consent of their parent / carer,
- Who are receiving treatment for their insomnia and/or mental health difficulties.

Consent

All assent and consent data will be collected via Research Electronic Data Capture (REDCap) — a web-based data capture system for research. Assent will be collected from 14 and 15-year-olds. Consent from their parent/carer will be collected also. The REDCap form will prevent young people under the age of 16-years from continuing if parent/carer consent has not been obtained. Consent will be collected from 16-18-year-olds. An electronic signature will be requested from all individuals to ensure we are collecting verified consent. To participate in an interview and/or provide data linkage will be optional. Upon turning 16 years old, participants will be re-approached and re-consented.

Materials:

All participants will receive STEP 1 (Sleep Solved) throughout their participation. Phone Downtime app infers sleep disturbance through movement and screen on/off events on phones using the Android operating system. Only users with an Android phone will be offered to use this app. If high levels of sleep disturbance persist at and beyond 6-weeks, the participant will be signposted to STEP 2 (adapted SHUTi programme). STEP 2 will include approximately 6 modules (in-depth advice) on sleep hygiene and mental health. Notably, Sleep Solved will be available to all participants throughout their participation. Some participants will also be signposted to STEP 3 (*Bite Back*).

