The in-depth qualitative interviews (estimated 60 for data saturation of participants at different time points) will explore participant understandings and attitudes towards sleep and how the boundaries/shape of the 'night-world' are influenced through interactions with others. We will explore how dilemmas get managed and moulded in everyday life, how the digital web-based application alters the landscape of sociality and expertise and whether the web-based application(s) had an impact and if that effect is altered by context. Questions will be explored through use of a topic guide, with changes made to questions based on iterative feedback from participants.

Participants who are interviewed may also be invited to keep diaries (audio/web logs, visual/written) to reflect on the behaviour change approaches (e.g., sleep restriction) which can be used as interview prompts. Details regarding how this data will be collected and stored is in Section 8 of the protocol.

5. Analyses

Analyses will be ongoing. Qualitative methodology will be applied to the audio and written data. Specifically, iterative thematic analysis grounded in participant views (concordant and discordant). Quantitative analyses will also be performed in the study. We will use the probable threshold for anxiety and depression of the RCADS at 6-weeks, 6- and 12-month follow up (adjusted for age/sex at birth) and conduct receive operator characteristic (ROC) analyses with appropriate confidence intervals to determine the sensitivity of insomnia screening. We will also compare anxiety and depression scores before and after each step and report whether we have found a signal.

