- If found to be experiencing sleep disturbance, participants will get free access to an adapted version of the SHUTi app which has been proven to work with adults. This app could also help them sleep better and therefore improve their mental and physical wellbeing.
- If after using the adapted SHUTi app participants continue to experience sleep disturbance or mental health symptoms, they will be signposted to local NHS support services and *Bite Back*, an evidence-based online positive psychology programme, which has been designed to improve resilience and wellbeing in young people aged 12-18.
- Participants might enjoy contributing to a national research project that could increase the quality of life for many young people.

Research benefits:

- Findings from a large observational mixed-methods study of young people's experiences of using sleep tracking plus our proposed stepped approach.
- A large young people's cohort (n=1000) with passive sleep data and self-completed mental health data.
- 10 research papers (e.g., uptake, effectiveness, epidemiology).

Benefits to wider society:

- Possible improvements in attendance and attainment in schools/colleges.
- Possible reduction in the use of NHS services for those participating.

8. Data Protection and Participant Confidentiality

Data will be entered into REDCap which is a secure system used by multiple institutions for large multicentre studies. Participants will enter their own data into REDCap. Participants will be sent a web link to REDCap which will only allow access to their data. REDCap also has an auto-log out system that will log participants out after 30 minutes if they have stopped using the database.

Data will be managed according to the following procedure. Participants will be allocated a unique research identification number. A list of names and corresponding identification numbers will be kept separately and securely on a password protected University of Bristol server or OneDrive folder. Personal information will be kept on consent forms which will have contact details. Consent forms will then be stored securely on a password protected University of Bristol server or OneDrive folder. Interview recordings (both audio and video files) will also be securely stored on a password-protected University of Bristol server or OneDrive folder.

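### The before/after comparison that answers research question 5 has no comparator, and for STEP 2 it is made in people selected for persistently high sleep disturbance, so scores can fall with no programme effect

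*Protocol*

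**What the plan says.** Research question 5 (Protocol section 3) asks: "Do mental health symptoms reduce following a) STEP 1 online advice on improving sleep hygiene and b) STEP 2 adapted modular SHUTi insomnia programme". Section 5 gives the method: "We will also compare anxiety and depression scores before and after each step and report whether we have found a signal".

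The design (section 4, Optimisation and Evaluation) is a single cohort: "An observational cohort with integrated qualitative methodology will provide the infrastructure to develop the web-based applications". No control or concurrent comparison group is described.

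Entry to the two steps differs (section 4, Materials):
- STEP 1: "All participants will receive STEP 1 (Sleep Solved) throughout their participation". Eligibility sets no insomnia threshold.
- STEP 2: "If high levels of sleep disturbance persist at and beyond 6-weeks, the participant will be signposted to STEP 2".

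ISI and RCADS are collected from all participants at baseline, 6 weeks, 6 months and 12 months (section 4, Data collection).

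**The concern.** A change within one group mixes any programme effect with everything else that moves scores between two surveys. For STEP 2 there is a further problem. The group is picked because sleep disturbance was high, and the 6-week survey can serve both as the point of selection and as the before score. Some of those people are at a temporary peak. If mood is temporarily worse when sleep is, their RCADS scores are also temporarily high and tend to drop back by the next survey.

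An inert STEP 2 could therefore yield a reported signal. The result may also feed publications, since effectiveness is among the example topics for the planned papers (section 7, Research benefits). For STEP 1 the stake is narrower: a change in the whole cohort, in either direction, could not be attributed to Sleep Solved.

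**Working it through.** **The plan's own figures.** 1000 × 0.80 = 800 retained. 800 × 0.30 = 240 with insomnia symptoms, and 240 × 0.75 = 180 also with mental health symptoms. Healthy sleepers: 800 − 240 = 560; 560 × 0.27 = 151 and 560 × 0.37 = 207. These agree with the stated 240, 180 and 150-210. The protocol gives no figure for the before/after comparison, so the inputs below are assumptions.

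**Assumptions.**
- ISI and RCADS are standard normal, each a stable part plus a transient part. The stable share (test-retest correlation) is ρ = 0.6 to 0.8.
- The ISI-RCADS correlation is 0.4 to 0.6, the same for the stable and transient parts. Call the transient one r_t.
- High means the top 30% of ISI, matching the protocol's 30% prevalence: c = 0.524, φ(c) = 0.348.
- Persistent means high at baseline and at 6 weeks. The before score is at 6 weeks and the after score at 6 months.
- There are 800 respondents, no programme effect and no time trend.
- A two-sided paired test at 0.05 is used as a yardstick. The protocol sets no such rule for a signal.

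**STEP 2, formulas.**
1. The same-occasion ISI-RCADS correlation exceeds the different-occasion one by g = (1 − ρ) × r_t.
2. Expected RCADS change in persistent cases: d = −g × φ(c) × [1 − Φ(c√((1 − ρ)/(1 + ρ)))] / P, where P is the proportion high on both occasions.
3. SE = SD/√n. The chance of a significant fall is close to Φ(|d|/SE − 1.96).

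**STEP 2, results.** SD is the simulated SD of change in the selected group, and n = 800 × P.

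| ρ, r_t | n | g | d (SD units) | SE | Chance of p<0.05 |
|---|---|---|---|---|---|
| 0.8, 0.4 | 169 | 0.08 | −0.08 × 0.348 × 0.431/0.211 = −0.057 | 0.63/√169 = 0.0485 | Φ(1.18 − 1.96) = 0.22 |
| 0.7, 0.5 | 152 | 0.15 | −0.15 × 0.348 × 0.413/0.190 = −0.113 | 0.76/√152 = 0.0616 | Φ(1.83 − 1.96) = 0.45 |
| 0.6, 0.6 | 138 | 0.24 | −0.24 × 0.348 × 0.397/0.1725 = −0.192 | 0.88/√138 = 0.0749 | Φ(2.56 − 1.96) = 0.73 |

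Simulation of one million people agrees with these: a fall of about 0.06 to 0.19 SD, significant in about 20% to 74% of studies, against a nominal 5%.

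**Sensitivity to the transient correlation.** By formula 1 the artefact depends on r_t. With r_t = 0.3 the fall is about 0.04 to 0.10 SD, significant in roughly 15% to 25% of studies. With r_t = 0, g = 0: the fall is 0.00 SD and the rate is 5%. If people were in fact selected on the 6-week score alone, the fall would be larger. At ρ = 0.7 and r_t = 0.5 it is 0.15 × 1.159 = 0.174 SD, where 1.159 = φ(c)/0.3.

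**STEP 1.** With no selection the same model gives an expected change of 0.00 SD.

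**Adjusted comparison.** With no effect, regressing the later RCADS on earlier RCADS and 6-week ISI in all respondents brings the false STEP 2 difference to about 0.00 SD when the stable and transient correlations are equal. When they differ, a small remainder can stay unless baseline ISI is also in the model.

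**The case against.** The strongest reply is that the protocol claims little. It describes an observational cohort for development, feasibility and acceptability; the research question says following, not because of; and section 5 promises only a signal. A separate analysis plan might specify the model. It is true that nothing in the text attributes the whole change to the step, and a reader who infers a stated causal claim goes beyond the wording. But section 5 does fix the type of comparison, and more detail on a within-group change would not supply a comparator. Section 4 itself supports SHUTi in adults by results against a control group.

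Two stronger readings are tempting and not supported:
- **Regression to the mean for STEP 1.** Restricting STEP 1 to the 240 with baseline insomnia gives false falls of 0.09 to 0.28 SD, significant in 62% to over 99% of simulated studies. The protocol states no such restriction. Everyone receives STEP 1, and in the unselected cohort this artefact is zero.
- **The 72% recovery figure.** The sample size text says that some healthy sleepers "will develop insomnia each year (of which 72% will recover". On its figures 0.72 × 151 = 109 to 0.72 × 207 = 149 would recover. It concerns new acute insomnia, assumed similar to adults, and not disturbance that has already persisted to 6 weeks, nor mood scores. In the whole cohort, new cases run against recovery, so the net drift has no fixed sign.

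It is also fair that selection is on sleep while the outcome is mood. The artefact is therefore indirect, and requiring persistence makes it smaller.

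**Conclusion.** The point holds for STEP 2 and, more narrowly, for STEP 1.

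- **STEP 2:** selection on persistently high sleep disturbance, with no comparator, can produce a fall in anxiety and depression scores with no effect. Its size is about 0.06 to 0.19 SD, significant in about 20% to 74% of studies, under the assumed correlations and a conventional 5% test. A reader might infer that a false signal is very likely. The range does not support that: the rate falls as the transient correlation weakens and returns to 5% when it is zero, and the documents do not say where in that range the study lies.
- **STEP 1:** the only defect is that time trends, attrition and repeat testing cannot be separated from effect.

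This limits what the comparison can be said to show. It does not undermine the cohort's feasibility, acceptability or detection aims.

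**What to change.** In section 5:

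1. **STEP 2.** Do not base the signal on raw change. Analyse all 6-week respondents, offered STEP 2 or not. Regress 6-month RCADS on baseline and 6-week RCADS, continuous 6-week ISI, age and sex, with an indicator for being offered STEP 2. If the offer also depends on the baseline level, add baseline ISI.
2. **Interpretation.** Treat this as a regression discontinuity only if one numeric 6-week ISI trigger is in fact applied to everyone. Section 4 speaks of sleep disturbance, the term it also uses for what the phone app infers, and of persistence at and beyond 6 weeks. Some in the reference group may thus be offered STEP 2 later. Unless a single trigger applies, report an adjusted, non-causal comparison.
3. **STEP 1.** Report the change as descriptive, with no effect claim.

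No new measurements are needed for this model, because ISI and RCADS are already collected from everyone at these surveys. The wording should cover participants over 18 at follow-up, for whom PHQ and GAD are listed. The cost is a change of analysis text, a less precise STEP 2 estimate than the raw change gives, and a weaker statement about STEP 1.

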The Phone Downtime app (for Android users only): We will apply machine learning algorithms based on time series characterisation, Bayesian methods for change point detection, and outlier detection enhanced with data visualisation to understand the population data structure (e.g., to find subpopulations and outliers). The data is relatively low frequency (estimated sleep timings and durations measured daily), so we expect existing algorithms to be adequate. We will use Bayesian learning algorithms to account for individual variation. Algorithms will be server-based enabling us to alert participants. Characteristics that predict when sleep patterns in an individual predict insomnia (and not a single broken night/weekend) are likely to be subject-dependent. Therefore, we will use a databased grouping of subjects with similar characteristics (using Bayesian inference to identify appropriate group sizes) and create models based on multiple individuals whilst providing variations in models that capture differences between subjects. Using the prevalence estimates of insomnia symptoms of 30%, a sample size of 236 is required for sensitivity and specificity of 0.9 (precision +/-5%). We will separate complete time courses to create model training and testing sets but retain each subject's whole data set within each group.

6. Project Management

The Core Management Group (CMG), consisting of the Chief Investigator (CI) and Project Manager (PM), will meet weekly to ensure the programme is delivering against its objectives. The Core Research Team (CRT) consisting of the CI, PM, co-applicants and researchers will be responsible for ensuring research delivery is integrated and timely. The CRT will meet every 6-weeks to discuss workstream milestones, outputs and risks, and PPIE outputs.

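### The 236 participants given for the Phone Downtime accuracy analysis yield about ±7 points on sensitivity at 95% confidence, not ±5; ±5 needs about 461.

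*Protocol*

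**What the plan says.** In Section 5 (Analyses), the Phone Downtime paragraph introduces its calculation with "Using the prevalence estimates of insomnia symptoms of 30" per cent and concludes that "a sample size of 236 is required for sensitivity and specificity of 0.9 (precision +/-5" per cent). It gives no confidence level and no formula.

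The rest of the Protocol gives some context. Section 4 (Sample size) calls the overall target of 1000 pragmatic and continues: "If we assume 20% attrition, recruiting 1000 young people will provide data" "on 800, of which 240 (30%) will have insomnia symptoms at enrolment". That is the same 30% prevalence, with expected counts but no interval width. Section 4 (Materials) restricts the app: "Only users with an Android phone will be offered to use this app". The Phone Downtime paragraph also says that participants will be divided into model training and testing sets, with each person's data kept together.

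**The concern.** The sentence names its prevalence, its expected accuracy and its precision, so the sample size can be checked directly. Sensitivity is estimated only in participants who have insomnia, and 30% of 236 is about 71 people. That is too few for a 95% interval of ±5 points around 0.9.

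This is the only place in the Protocol where a sample size is tied to a stated precision. A reader who wants to know whether the passive-sensing data can support an accuracy claim has only this figure to rely on. If 236 is taken as sufficient, sensitivity will be reported less precisely than the Protocol says. The shortfall falls on the measure that depends on the smaller group.

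**Working it through.** **Inputs**
- Prevalence 0.30 (Section 5, and consistent with Section 4).
- Expected sensitivity and specificity 0.9 each (Section 5).
- Half-width d = 0.05 (Section 5).
- Confidence level: not stated. Assumed 95% two-sided, z = 1.96; other levels are shown below.

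**Formula** (normal approximation)
- Sensitivity: N = [z² × 0.9 × 0.1 / d²] / 0.30
- Specificity: N = [z² × 0.9 × 0.1 / d²] / 0.70

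**Attempt to reproduce 236 at ±5 points**
- Cases needed: 3.8416 × 0.09 / 0.0025 = 138.3.
- Sensitivity: 138.3 / 0.30 = 461 (464 if cases are first rounded up to 139).
- Specificity: 138.3 / 0.70 = 197.6, so 198.
- Both together, as the sentence claims: 461, which is 461 / 236 = 1.95 times the stated number.

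236 is not reproduced.

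**What does reproduce 236**
- With d = 0.07: 3.8416 × 0.09 / 0.0049 = 70.56 cases; 70.56 / 0.30 = 235.2, rounded up to 236.

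**Precision at N = 236**
- Cases: 236 × 0.30 = 70.8. Half-width for sensitivity: 1.96 × √(0.09 / 70.8) = 0.070.
- Non-cases: 236 × 0.70 = 165.2. Half-width for specificity: 1.96 × √(0.09 / 165.2) = 0.046.
- With 64 of 71 cases detected, the 95% Wilson interval is 81.0% to 95.1% and the Clopper-Pearson interval is 80.7% to 95.9%.

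**Other confidence levels, ±5 points on sensitivity**

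| Confidence | N required |
|---|---|
| 80% | 197.1 |
| 85% | 248.7 |
| 90% | 324.7 |
| 95% | 461.0 |
| 99% | 796.2 |

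At N = 236 the implied level is that of z = 0.05 / √(0.09 / 70.8) = 1.40, about 84%.

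**Other routes tried**
- Better-behaved intervals ask for more: Wilson needs 141 cases (470 participants), and Clopper-Pearson 158 cases (about 527).
- A finite-population correction to 461 gives about 293 for a population of 800 and 316 for 1000.
- Specificity alone multiplied by 1.2 gives 237 to 238, but this ignores sensitivity.
- 99% confidence without dividing by prevalence gives 239, but this ignores the 30% that the sentence says it uses.

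**The case against.** The strongest reply is that little depends on the figure. The study aims for 1000 participants and 236 is nowhere a recruitment target, cap or stopping point. The app work is largely exploratory model development, and no success rule is attached to the number. If many Android users contribute data, the achieved precision could be ±5 points or better. Specificity already meets the target at 236. The confidence level is also an assumption, because the only mention of intervals, "with appropriate confidence intervals to determine the sensitivity of insomnia screening", concerns the separate ROC analysis of insomnia screening.

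Most of this stands as a limit on the consequences. The Android share is not given, so the Protocol does not show whether 461 would be reached. Of the 800 expected to provide data, 461 is 57.6% and 236 is 29.5%, so the two figures imply quite different requirements for Android uptake. If accuracy is estimated only in a held-out part of the sample, precision is worse. As an illustration, half of 236 gives 35.4 cases and 1.96 × √(0.09 / 35.4) = ±9.9 points.

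None of this makes the sentence true. It names 236 as the number required for ±5 points on both measures, and none of the conventional confidence levels gives that result. An analysis plan could add detail but could not reconcile the two numbers.

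**Conclusion.** The stated figure is wrong as written. At 95% confidence, with the Protocol's own prevalence and accuracy, 236 participants give ±7.0 points on sensitivity and ±4.6 on specificity. For ±5 on both, 461 are needed, nearly double. The conclusion rests on the 95% level and the normal approximation. Wilson and exact intervals raise the requirement, and a lower level would have to be about 84% to justify 236.

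The exact match at ±7 points suggests that the precision was misprinted or carried over from another calculation, though the Protocol does not show how 236 was obtained. The error concerns sensitivity only, and its effect on the final precision cannot be determined without the number of Android users who provide evaluable data.

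**What to change.** Correct the one sentence in Section 5 in either of two ways, stating 95% confidence:

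1. Keep the number: 236 participants give about ±7 points for sensitivity and ±4.6 points for specificity, if both are 0.9 and prevalence is 30%.
2. Keep the precision: 461 participants are required for ±5 points on sensitivity (464 if cases are rounded up to 139); specificity alone needs 198.

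The first is the smaller change and needs no further recruitment. The second should come with the expected number of Android users, so that a reader can see whether 461 is attainable. In either case, say that the number counts Android users with evaluable app data whose predictions come from models not trained on them. The editing cost is one sentence. The price is a less favourable figure: wider stated precision or a larger required sample.
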